#### **10.1.3 Recording and Reporting of Serious Adverse Events and Adverse Events of Special Interest**

Every SAE/AESI (regardless of severity and causality) that occurs once the patient has signed the ICF and through 14 days after the final dose of study drug, should immediately and not later than within 24 hours of knowledge of the event, be reported by the Investigator or delegate using the SAE/AESI report form.

Report of a SAE/AESI must include at least the following information:

- Patient identification information (study number, site number, and date of birth [as per local country requirements for data protection])
- The last study drug administration date
- The diagnosis of the event with the description (or a brief description of signs/symptoms/clinical course if the diagnosis is not available) and the date of onset

- The action used to treat the event (i.e., treatment medications, temporary discontinuation)
- The reason(s) for considering the event serious
- The relationship of the event to the study drug or to the study procedure (i.e., the Investigator's assessment of causality)
- A brief narrative of the SAE/AESI

Follow-up reports including all new information obtained of the subsequent course of the SAE/AESI must be prepared and the information collected in the SAE/AESI report form submitted to the CRA, and [REDACTED]

[REDACTED] by e-mail within 24 hours of knowledge of the event.

The pharmacovigilance manager (PVM) or the CRA may contact the Investigator to obtain further information on a reported SAE/AESI. The investigator/investigative staff must respond to any request for follow-up information or answers to questions regarding the SAE/AESI within the same timelines as for initial reports.

The PVM reports the occurrence of the SAE/AESI and follow-up to the Sponsor's Medical Monitor for medical assessment of the case.

Should an outcome of death occur within the study period or within 14 days after the last administration of study drug, an SAE/AESI report form should be completed including the main and contributory causes of death.

All SAE/AESI reports must be e-mailed to the following e-mail address within **24 hours**:

[REDACTED]

If email is unavailable, SAEs/AESIs may be transmitted via fax to the following number:

[REDACTED]

#### **10.1.4        Notification of Suspected Unexpected Serious Adverse Reactions**

A suspected unexpected serious adverse reaction (SUSAR) is an SAE that occurs in a patient, the nature or severity of which is not expected per the applicable product information. The elobixibat Investigator's Brochure will serve as the reference safety information for this study.

Reporting and tracking of SUSARs will be in accordance with all applicable competent authority regulations. The IRBs and all Investigators involved in this study will be informed according to local requirements.

## **10.2      Laboratory Values, Vital Signs, Physical Examinations, and Other Safety Assessments**

### **10.2.1      Laboratory Assessments**

Samples will be collected for clinical chemistry, hematology, urinalysis, and other lab assessments at the time points specified in [Table 1](#). The parameters assessed are presented in [Table 2](#). All samples will be processed and transported to a central laboratory per instructions in the study reference manual.

The observed values will be recorded and assessed as “normal” or “abnormal not clinically significant” or “abnormal clinically significant.”

Additional blood samples may be needed due to follow-up of an abnormal value or analysis failure. The blood samples collected for safety laboratory analysis will be destroyed after the analyses have been completed.

Stored blood samples for future testing are detailed in Section [9.2.4](#).

**Table 2: Laboratory Parameters**

CLINICAL CHEMISTRY (FASTING)	HEMATOLOGY/COAGULATION	URINALYSIS

 
• Albumin
 
• ALT
 
• Alkaline phosphatase
 
• Amylase
 
• AST
 
• Bicarbonate
 
• Blood urea nitrogen
 
• Calcium
 
• Chloride
 
• Creatine kinase
 
• eGFR by MDRD (screening only)
 
• Gamma-glutamyl transferase
 
• Glucose
 
• Hemoglobin HbA1C
 
• Inorganic phosphorus
 
• Lactate dehydrogenase
 
• Lipase
 
• Potassium
 
• Sodium
 
• Total bilirubin
 
• Total protein
 
• Uric acid
 
	
 
• Hematocrit
 
• Hemoglobin
 
• Platelet count
 
• Red blood cell count
 
• White blood cell count and differential (neutrophils, eosinophils, basophils, lymphocytes, and monocytes)
 
 
Manual microscopic review is performed only if white blood cell count and/or differential values are out of reference range.
 
 
• International normalized ratio (INR)
 
• Prothrombin time (PT)
 
	
 
• Bilirubin
 
• Blood
 
• Glucose
 
• Ketones
 
• Leukocyte esterase
 
• Microscopy including leukocytes (performed only as needed based on positive dipstick test results)
 
• Nitrites
 
• pH
 
• Protein
 
• Specific gravity
 
• Urobilinogen
 

*(Continued on next page)*

LIPID PROFILE (FASTING)	OTHER TESTS	ENDOCRINOLOGY

 
• Apolipoprotein A1
 
• Apolipoprotein B
 
• Chylomicron cholesterol
 
• Chylomicron triglycerides
 
• High-density lipoprotein (HDL) cholesterol
 
• Lipoprotein(a) cholesterol
 
• Low-density lipoprotein (LDL) cholesterol
 
• LDL triglyceride
 
• Non-high-density lipoprotein cholesterol
 
• Total cholesterol
 
• Triglycerides
 
• Very low-density lipoprotein (VLDL) cholesterol
 
• VLDL triglyceride
 
• Lanosterol
 
• Beta-sitosterol
 
	
 
• High-sensitivity C-reactive protein (CRP)
 
• C4
 
• Fibroblast growth factor-19 (FGF-19)
 
• Fibrosis and inflammation markers: FIB-4, APRI, and NAS
 
• Glucagon-like peptide-1 (GLP-1)
 
	
 
• Follicle-stimulating hormone
 
• Homeostatic model assessment-insulin resistance
 
• Insulin
 
• Thyroxine
 
• Triiodothyronine
 
• Thyroid-stimulating hormone
 
• Free fatty acids
 
• Adipose tissue insulin resistance
 
• Adiponectin
 

BILE ACIDS (FASTING)	PREGNANCY	SEROLOGY

 
• Total bile acids
 
	
 
• Serum
 
• Urine
 
	
 
• Hepatitis B virus surface antigen
 
• Hepatitis C virus antibody and ribonucleic acid
 

 LDL-cholesterol will be determined by calculation when triglyceride levels are less than or equal to 400 mg/dL, LDL-C will be determined by preparative ultracentrifugation (PUC) when triglyceride levels are greater than 400 mg/dL.

 A postmenopausal state is defined as no menses for ≥12 months without an alternative medical cause. A follicle-stimulating hormone level in the postmenopausal range will be used to confirm a postmenopausal state in women ≤55 years of age, performed at Screening visit only.

 Thyroid function test will be performed during Screening visit only.

## **10.2.2 Individual Patient Safety Monitoring**

### **10.2.2.1 Liver Monitoring**

Strategies to monitor markers of liver disease throughout the study are outlined below where the ULN will be based on central laboratory reference values for age and gender. Patients will be monitored as described below for drug-induced liver injury from randomization to 2 weeks following the last administration of study drug.

#### **Elevated ALT**

- ALT  $>5 \times$  ULN or  $>3 \times$  Baseline (if ALT elevated at Baseline): repeat AST, ALT, total bilirubin, alkaline phosphatase (ALP), and INR within 72 hours of receipt of the result and closely monitor the patient. If liver enzyme elevation is confirmed, interrupt the study drug. The study drug can be restarted only if a competing etiology is identified or liver tests return to Baseline.

#### **Elevated AST**

- AST  $>5 \times$  ULN or  $3 \times$  baseline (if AST elevated at baseline): repeat AST, ALT, total bilirubin, ALP, and INR within 72 hours of receipt of the result and closely monitor the patient. If liver enzyme elevation confirmed, interrupt the study drug. The study drug can be restarted only if a competing etiology is identified or liver tests return to Baseline.

#### **Elevated Total Bilirubin**

- Total bilirubin  $>2 \times$  ULN or  $>1.5 \times$  Baseline (if total bilirubin elevated at Baseline), regardless of ALT or AST levels: repeat AST, ALT, total bilirubin, ALP, and INR within 72 hours of receipt of the result and closely monitor the patient. If liver enzyme elevation confirmed, interrupt the study drug. The study drug can be restarted only if a competing etiology is identified or liver tests return to Baseline.

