### **7.2.3            Withdrawal of Patients**

Patients will be informed that they have the right to withdraw from the study at any time, without prejudice to their medical care, and that they are not obliged to state their reasons.

Any withdrawal, and reasons for withdrawal, must be fully documented in the electronic case report form (eCRF) and source documents and the patient followed by the investigator/investigative staff. Even after the study is completed at the Follow-Up visit, the investigator/investigative staff will, regardless of reason for withdrawal, record any patient data they receive concerning serious adverse events (SAEs), and all drug-related non-serious AEs, and report these in the eCRF. Withdrawn patients will not be replaced.

Patients will be withdrawn in the following circumstances:

- A patient's desire for withdrawal for any reason
- Lost to follow-up (every effort must be made to contact the patient; a certified letter must be sent)
- An AE that, in the opinion of the Investigator, necessitates withdrawal
- Death
- A patient's substantial noncompliance (study drug compliance) or protocol violation
- An Investigator's opinion that continuing the patient in the study is not appropriate. The Investigator may withdraw a patient at any time if it is considered to be in the patient's best interest

A patient who withdraws from treatment prematurely will have EOT (Visit 6) assessments at the time of withdrawal and a Follow-Up assessment (Visit 7) approximately 2 weeks following the last dose of study drug, and the patient will be recorded as withdrawn.

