#### **Other Clinical Symptoms**

- Clinical signs of hepatitis or indicators of immunological reaction (e.g., nausea, vomiting, right upper quadrant pain, loss of appetite, dark urine, jaundice, rash,

eosinophilia >5% or symptoms/signs of hepatic decompensation): discontinue the study drug and repeat AST, ALT, total bilirubin, ALP, and INR within 72 hours and closely monitor. Other causes of hepatitis should be excluded.

When close monitoring of a patient is not possible while the patient is on study drug, interrupt the study drug and closely monitor the patient.

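### The bilirubin rule triggers whatever the ALT or AST, yet orders interruption only on a confirmed liver enzyme elevation, so a confirmed isolated bilirubin rise has no mandated stop

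*Protocol*

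**What the plan says.** Section 10.2.2.1 (Liver Monitoring) of Protocol v3.0 sets individual rules intended to catch drug-induced liver injury. They cover ALT, AST, total bilirubin and clinical symptoms.

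The total bilirubin rule fires above 2 × ULN, or above 1.5 × Baseline ("if total bilirubin elevated at Baseline), regardless of ALT or AST levels"). The site must then "repeat AST, ALT, total bilirubin, ALP, and INR within 72 hours of receipt of the result and closely monitor the patient". Next comes the interruption step: "If liver enzyme elevation confirmed, interrupt the study drug". The rule ends: "The study drug can be restarted only if a competing etiology is identified or liver tests return to Baseline".

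The ALT rule has nearly the same interruption step: "If liver enzyme elevation is confirmed, interrupt the study drug". The AST rule has it in exactly the form used for bilirubin.

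Two further mandatory stops appear under Other Clinical Symptoms:

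- Drug is discontinued for clinical signs of hepatitis or indicators of an immunological reaction. The examples include "right upper quadrant pain, loss of appetite, dark urine, jaundice, rash" and eosinophilia above 5%.
- "When close monitoring of a patient is not possible while the patient is on study drug, interrupt the study drug".

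Section 7.2.3 adds a discretionary route: "The Investigator may withdraw a patient at any time if it is considered to be in the patient's best interest".

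**The concern.** The trigger declares transaminases irrelevant, and the action then makes liver enzymes decisive. In the ALT and AST rules the interruption sentence covers the analyte that set the rule off. In the bilirubin rule it does not. The likeliest explanation is that the sentence was carried over from the rules above it.

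The stake is patient safety, not inference. If the sentence is followed as written, a site can keep dosing a patient whose bilirubin is confirmed above the trigger without committing a protocol deviation. Two of the up to 15 sites could also handle the same result differently, one reading for intent and one reading the words.

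**Working it through.** There is no figure in the plan to reproduce. The check reads the rules as decision logic and asks whether any of them forces an interruption for an isolated bilirubin rise.

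**Step 1. Compare trigger and interruption condition in the three laboratory rules.**

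| Rule (10.2.2.1) | Trigger | Literal condition for interruption | Can the triggering analyte meet it? |
|---|---|---|---|
| ALT | >5 × ULN, or >3 × Baseline if raised at Baseline | confirmed liver enzyme elevation | Yes, ALT is an enzyme |
| AST | >5 × ULN, or 3 × Baseline if raised at Baseline | the same | Yes, AST is an enzyme |
| Total bilirubin | >2 × ULN, or >1.5 × Baseline if raised at Baseline | the same | No, bilirubin is not an enzyme |

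**Step 2. Look at the repeat panel.** It has five tests. Three are enzymes (AST, ALT, ALP) and two are not (total bilirubin, INR). The panel re-measures bilirubin, but a second high bilirubin does not satisfy the condition as worded.

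**Step 3. Run one patient through every rule.** Take bilirubin confirmed above the trigger; AST, ALT and ALP not elevated; no clinical signs or immunological indicators; close monitoring feasible.

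- ALT rule: not triggered.
- AST rule: not triggered.
- Bilirubin rule: triggered. Repeat panel and close monitoring are required, but the interruption condition is not met.
- Clinical symptoms rule: not triggered. A patient with jaundice or dark urine would be stopped here.
- Rule for when close monitoring is not possible: not triggered.
- Section 7.2.3: withdrawal at the Investigator's discretion only.
- SAP: no individual stopping rule. Section 3.4 only summarises and lists laboratory data.

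The text therefore mandates two actions (repeat panel, close monitoring) and no interruption.

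**Step 4. Check that such a patient can be in the trial.** Under inclusion criterion 3b the metabolic-syndrome route sets no minimum ALT or AST. Exclusion criterion 4a sets only a ceiling of 5 × ULN for each. No entry criterion concerns ALP. Enrolment with normal enzymes is therefore possible.

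**Step 5. Put the trigger in context.** Exclusion criterion 4c bars total bilirubin above ULN except in established Gilbert's syndrome. A patient without Gilbert's thus qualifies at no more than 1 × ULN, and a value above 2 × ULN is more than 2 ÷ 1 = 2 times the highest qualifying value.

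**The case against.** The strongest reply is that nobody would read the sentence literally. The rule is headed for bilirubin and triggered only by bilirubin, and a repeat test can only confirm a rise already seen. A sensible site would take the sentence to mean that drug stops if the bilirubin rise is confirmed. That may well be the intent, but it has to be inferred. The restart clause is limited support for it: the ALT and AST rules carry the same clause, and it governs what follows an interruption without ordering one. It also refers to liver tests, a broader term than liver enzymes, so a careful reader could think the narrower words were deliberate.

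If they were deliberate, requiring enzyme evidence before stopping drug is an arguable choice. But the rule gives no reason for it, and it sits badly with a trigger that sets ALT and AST aside.

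The gap is also narrow, and several points that narrow it stand:

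- The clinical signs are given as examples, not a closed list, and they include a laboratory indicator (eosinophilia).
- No threshold is given for an enzyme elevation. If it means merely above normal, many NAFLD/NASH patients could meet the condition through a chronically raised ALT. That shrinks the gap, but it would make interruption depend on background enzyme status instead of on the bilirubin.
- A clinically significant laboratory deterioration can be recorded as an AE, and an AE can lead to withdrawal. These routes are discretionary.
- About 23 patients are planned on active drug, and nothing in the documents says how often the combination would occur.

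These points limit the consequence. They do not make the sentence correct.

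**Conclusion.** The concern holds. As written, the bilirubin rule's interruption step names the wrong analyte, and no other rule in Protocol v3.0 or the SAP mandates interruption for a confirmed isolated bilirubin rise.

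Four conditions must coincide: bilirubin confirmed above the trigger; no AST, ALT or ALP elevation; no clinical signs or immunological indicators; and close monitoring possible. Retesting and close monitoring still protect that patient.

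The conclusion rests on reading the sentence literally and on the usual meaning of liver enzymes (AST, ALT and, on this panel, ALP). No event rate is available, so none is estimated. It should be fixed because it is a safety instruction sites act on directly. It does not threaten the trial's results.

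**What to change.** In the bilirubin rule only, replace the interruption sentence with: *If the total bilirubin elevation is confirmed, interrupt the study drug.* Leave the ALT and AST rules and both bilirubin thresholds unchanged.

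No separate Gilbert's threshold is needed. The restart clause already allows drug to resume once another cause is identified, which covers the Gilbert's patients admitted under criterion 4c. In a known Gilbert's patient the interruption may be reversed almost at once, which is a small inconvenience.

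The change is one sentence in an amendment or a safety clarification letter. It needs no new test, because bilirubin is already on the repeat panel. The price is an occasional temporary interruption in a patient whose rise proves benign.

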#### **Other Clinical Symptoms**

- Clinical signs of hepatitis or indicators of immunological reaction (e.g., nausea, vomiting, right upper quadrant pain, loss of appetite, dark urine, jaundice, rash,

eosinophilia >5% or symptoms/signs of hepatic decompensation): discontinue the study drug and repeat AST, ALT, total bilirubin, ALP, and INR within 72 hours and closely monitor. Other causes of hepatitis should be excluded.

When close monitoring of a patient is not possible while the patient is on study drug, interrupt the study drug and closely monitor the patient.

#### **10.2.3 Demographics/Medical and Surgical History**

Demographic information per country regulations (age, full date of birth, gender, race, and ethnicity), along with medical and surgical history, will be obtained and recorded in the eCRF at Visit 1.

Medical and surgical history will be entered in the eCRF at Visit 1. This includes date of diagnosis of NASH/NAFLD including liver biopsy results for biopsy-confirmed NASH patients within 6 months of screening, ongoing medication, any surgery performed, and any other diagnoses.

#### **10.2.4 Physical Examination**

A physician or suitably trained qualified assistant will perform a complete physical examination at Screening, at Visit 2, and at Visit 6. Height (Screening only), weight, waist circumference, and waist-to-hip ratio will also be collected. BMI will be calculated based on height and weight.

A complete physical examination will include assessment of general appearance, eyes, ears, nose, throat, head/neck/thyroid, lymph nodes, cardiovascular, lungs/chest, abdomen, genitourinary, extremities, skin, musculoskeletal, neurologic, and other.

#### **10.2.5 Vital Signs**

Evaluation of vital signs will be performed at all visits. This includes blood pressure (systolic and diastolic), pulse, respiratory rate, and oral temperature.

#### **10.2.6 12-Lead ECG**

A 12-lead ECG will be performed at the Screening visit and the EOT visits.

**10.2.7 Overdose**

Elobixibat is minimally absorbed and has a very low systemic availability. It is not known whether elobixibat can be removed from the systemic circulation by dialysis. There are no known antidotes for elobixibat overdoses. If an overdose occurs, the patient should be carefully monitored and treated with supportive therapy.

**10.2.8 Pregnancy**

If a pregnancy is discovered in a female patient enrolled in the study, the patient will be immediately discontinued from the study drug, if applicable, and will attend the same visits as a prematurely withdrawn patient. If the pregnancy is discovered after completion of the treatment period, the patient will continue in the study per protocol. If a pregnancy occurs in a male patient's partner at any time during the study, the pregnancy should also be reported and followed.

If the patient has been dosed with the study drug, the pregnancy must be recorded on the appropriate form and submitted to the PVM (Section 10.1.3) within 24 hours of learning of the pregnancy.

The pregnancy should be followed to determine outcome, including spontaneous termination, details of birth and presence of any birth defects, congenital anomalies or newborn or maternal complication. While pregnancy itself is not considered to be an AE or SAE, any pregnancy complication or elective termination of a pregnancy for medical reasons will be reported as an AE or SAE. A spontaneous abortion (occurring at <22 weeks gestational age) or still birth (occurring at >22 weeks gestational age) is always considered to be an SAE and will be reported as such.

Any post-study pregnancy related SAE considered reasonably related to the study intervention by the investigator will be reported as described in Section 10.1.3. While the investigator is not obligated to actively seek this information in former study participants, he or she may learn of an SAE through spontaneous reporting.

## **11. STATISTICAL EVALUATION**

All personnel involved with the analysis of the study will remain blinded until database lock for the double-blind treatment period and until major protocol violations have been identified.

All statistical analyses will be performed using SAS version 9.3 or higher.

### **11.1 Sample Size and Power**

Due to the exploratory nature of this study, no formal power calculations were used to determine the sample size. The number of subjects (46 patients in total, 23 patients per treatment group) was chosen based on clinical experience with other similar proof-of-concept studies.

### **11.2 Statistical Methods**

#### **11.2.1 Statistical Analysis Populations**

##### **ITT Population**

The intent-to-treat (ITT) population will include all patients who are randomized in the study and receive at least 1 dose of study drug. The ITT population will be used for all efficacy analyses based on the treatment randomized unless otherwise specified.

##### **Per Protocol Population**

The per protocol (PP) population will include all ITT patients who finish Visit 7/EOT with valid LDL-C measurements and do not have any major protocol deviations.

Allocation of patients to the PP analysis set will be performed before unblinding of the study.

##### **Safety Population**

The safety population will include all patients who are randomized and receive at least 1 dose of study drug and will be used for all safety analyses based on the treatment received.

## **11.2.2 Methods of Statistical Analyses**

### **11.2.2.1 General Principles**

Summary statistics (number of patients, mean, standard deviation, median, minimum, and maximum) at all visits and change or percent change from Baseline will be provided for efficacy and safety continuous variables. Count and frequency will be used to tabulate categorical variables.

